#### Surveys

Participants will complete the first weekly "long-term" survey (Table 2, third column) on REDCap.

#### Communication to primary diabetes provider

The research team will send a letter by secure clinic fax to diabetes care provider (Appendix 19) that informs them of their patient's participation, contains share code to view real-time glucose values, advises that biometric data including CGM and insulin are available upon request when the participant completes the protocol, and that our Data and Safety Monitoring Plan includes contacting them if there are any exercise-associated concerns related to hypoglycemia, diabetic ketoacidosis, or health risks.

# **Monitor Symptoms**

Same as visit 1.

# **VISIT 3 (Day 15)**

#### Surveys

Participants will complete the second weekly "long-term" surveys (Table 2, third column).

August 13, 2024

Version #7

#### **Blood pressure**

Repeat visit 2 procedures.

#### **Monitor Symptoms**

Same as visit 1.

#### **VISIT 4 (Day 22)**

# **Monitor Symptoms**

Same as visit 1.

# **Start of Intervention**

Participants will download and be oriented to use the GlucoseZone™ (New Haven, CT) mobile application that delivers the digital intervention. The intervention is designed to target 150 minutes of weekly exercise, in accord with recommendations. Participants utilize exercise videos with biometrically-driven feedback coaching.

#### Data Captured by App

**Daily context each morning -- Appendix 8a:** 1) prior day hypoglycemia episodes; 2) recent clinical events (asked every 2 weeks only); 3) fear of hypoglycemia previous night and coming day; 4) sleep quality and nocturia previous night; 5) competing demands and exercise plan for the day.

Pre- and mid-exercise context captured in conjunction with videos – Appendix 8b & 8c and passive data from app and sensors:  $\underline{1}$ ) carbohydrates taken;  $\underline{2}$ ) insulin dosing;  $\underline{3}$ ) weather;  $\underline{4}$ ) day of the week;  $\underline{5}$ ) exercise instructional video selected; 6) exercise performance metrics.

**24hr passive data from sensors –** 1) Continuous blood glucose; 2) Physical activity outside of exercise videos

The app uses this biometric data to give exercise guidance, as described in the funded grant submission (1K01DK129441) and below

Tool #1: Access to a library of 200 exercise videos following brief human orientation consultation (Appendix 18b). Our ~200 exercise videos (GlucoseZone™, New Haven, CT) include a combination of aerobic, resistance, flexibility, and balance exercises, in accord with American Diabetes Association recommendations. They can be filtered by difficulty level, duration, type of exercise (aerobic vs. resistance), muscle groups, mobility limitations (knee-friendly, shoulder-friendly, chair-based), indoor/outdoor, and home equipment availability. Using these filters, participants can select single sessions or 30-session series that progress in difficulty and duration. Participants self-schedule exercise time in their home environment or outdoor guided walking routes. Participants may select routines requiring no equipment, use a \$10 set of resistance bands we recommend, use their dumbbells or household items like frozen water bottles. A trained exercise physiologist (EP) from the research team ([name],) will guide downloading the app, discuss exercise levels, goals and safety (Appendix 22a), and recommend starting videos and series. This orientation will be audio-recorded and combined with later interviews for qualitative analysis (Sect 7.2.1, hypothesis 2-3). A consultant from the manufacturer of GlucoseZone (Fitscript LLC; [name] [name] or [name]) will be available for assistance with downloading, navigating, or troubleshooting the app.

August 13, 2024

Version #7

Tool #2: Daily just-in-time adaptive text messages to overcome exercise barriers on vulnerable days. Just-in-time adaptive messaging is "an intervention that adapts the provision of support (e.g., the type, timing, intensity) over time to an individual's changing status and contexts with the goal to deliver support "at the moment and in the context that the person needs it most and is most likely to be receptive." From "data captured by app" (above, Appendix 8) the app will extract data to generate just-in-time adaptive messages. Specifically, the app organizes these data on a dashboard accessible to Yale staff. When a Yale staff member monitors this dashboard daily for exercise safety as described in the DSMP (Sect 8.7, "tracking") they export the contents onto the Yale Secure Server and enter them into our machine-learning code using Python to generate a supportive message (or confirmation that no message is needed that day). The staff member relays this information to the EP [name] who edits the message as needed according to standard of care T1D exercise guidelines then sends the message to the participant through the GlucoseZone app.

The exported data include firstly exercise adherence, by tracking usage of exercise guidance (videos or guided outdoor walking). Fitbit heart rate readings verify exercise timing, duration, and intensity. The Borg Rating of Perceived Exertion prompt captures intensity for non-aerobic exercises such as weightlifting (Appendix 8c). The extracted data also include contextual variables that may predict vulnerability to missing exercise: 1) 24hr blood glucose derived from interstitial vales sampled every 5min by the CGM and expressed by consensus metrics (coefficient of variation, mean, % time >180, 70-180, <70mg/dL). 2) Fear of hypoglycemia the previous night and coming day (Appendix 8a). 3) Sleep Quality the previous night from self-report (Appendix 8a) and Fitbit (sleep time overestimation ~10%); 4) Competing demands and exercise plan (Appendix 8a); 5) Weather; (temperature, humidity, windchill) captured using GPS location and the National Weather Service API; 6) Day of the week (weekday vs. weekend). 7) Insulin dosing (including entered carbohydrates) from the participant's device (InPen, Tandem, Omnipod, or Medtronic). 8) Physical activity outside of exercise videos; captured by the proprietary Fitbit algorithm (intensity classification accuracy 85%, step counts ±3%;).

The above markers of individual context, day of the week, and between-participant characteristics, including demographics and clinical characteristics that can impede exercise (body composition, mobility limitations), will be exported from GlucoseZone to our Yale Secure Server for processing by our machine-learning code. The code is programmed to identify predictors of exercise "lapse," defined as the 3rd missed day of the week or 2nd consecutive missed day given that the goal is 150 min/week spread over ≥5 days. Thereafter, when the code detects these predictors, the research assistant running the code will signals the exercise coach to edit then send a specific encouragement message. E.g., if high blood glucose variability is a vulnerable state predictor, the just-in-time message meeting its occurrence would read: "Sometimes blood glucose can go up and down. You can still be active using the strategies you and your provider have discussed." This encouragement does not extend to suggestions of specific exercises or managing low blood glucose.

The mathematical basis of the code is a binary classification model of exercise lapse using Python scikit-learn package v. 0.19.098, including random forests and gradient boosted tree ensembles (such as XgBoost99). We have completed analyses that train the model at the group level which was aim 2 of our prior protocol (HIC #2000025992). Briefly, we collected data on blood glucose, insulin dosing, fear of hypoglycemia, sleep, illness, and exercise occurrence. We ran two types of machine learning – random forest and dense neural network -- to predict exercise lapses (i.e., days without exercise) based upon prior days' blood glucose, fear of hypoglycemia, sleep, and illness. The data were randomly split where 80% of persondays were used to train the model and the other 20% were used to test the model. The present study will use the random forest model which had the highest accuracy (79%). Its sensitivity to predict exercise lapses was 83% and specificity was 71%. A **confidential** draft of the full manuscript describing the development is included (Appendix 20). These accuracy metrics, while limited, are better than the non-Al alternative of sending an encouraging message every day without any attempt to select for the most vulnerable days. Doing so can lead the participants to develop alarm fatigue and silence the notifications.

These models have been pruned to reduce the complexity of the final classifiers and avoid overfitting the training data. This group-level model (Appendix 9a) will be the starting point for training a person-level model for each participant via supervised transfer learning methods during the present study to give the participant tailored prompts. This strategy mitigates the shortness of the timeframe (4 weeks) to train each

August 13, 2024 Version #7

person's model. At the end of the study, the data will first be used as an independent sample to validate the pilot group-level model. Second, they will be combined with the pilot data for a larger sample size to assess potential covariates, including pump vs. injection users, prior CGM usage, and age. If needed, separate models for subgroups can be established in the subsequent beta version of the app. Models are evaluated by the number of lapses required to train person-level models to reach acceptable accuracy (receiver-operator characteristic AUC .80, or precision-recall AUC .80 if <20% of days are lapses), thus estimating a "learning window" before users can expect adaptive feedback. We can anticipate this learning window by programming the app to utilize a simplified algorithm (e.g., chosen from a bank according to an *a priori* hierarchy of barriers present) until adaptive feedback starts. For instance, the example at the end of the previous paragraph would be utilized based on the detection of high blood glucose variability, even if the model has not yet established high blood glucose variability as a vulnerable state predictor.

The messages will go through expert human review and edits by the EP prior to sending to the participants. Differences between the algorithm-generated and human-edited messages will be tabulated for analysis at the end of the study (Sect 7.2, Hypothesis 1-3-1).

Tool #3: Personalized review of safety hazard occurrences around exercise and tips to avoid them. The GlucoseZone cloud will apply heuristic codes to the exercise and CGM data to recognize common patterns that contribute to glycemic regulation (Table 3). These patterns were selected using a list in international consensus guidelines for the entire T1D population pared down to ones observed occurring in our pilot study. The GlucoseZone cloud will send participants weekly reports to summarize their patterns, corresponding follow-up tips, daily CGM tracings with indicated exercise times, and weekly summary statistics. The above patterns may occur less commonly than expected (≥1 of the above patterns occurring in ≥80% of person-weeks) or differ in occurrence by covariates noted above like pump vs. injection users, prior CGM usage, and age. In that case, we will examine the data for other more commonly occurring patterns to include in this tool in the next version. CGM tracking of people with T1D in the earliest stages of exercise uptake is novel, so some new patterns are expected.

Table 3. Example summary of exercise safety hazards with tips to avoid them.					
Pattern	Definition	Times of occurrence	Follow-up Tip		
Failure to take adequate	(Blood glucose <70 mg/dL	Monday 9:43am	A		
carbohydrate	at the start of exercise)	Wednesday 11:16am			
supplementation relative	OR				
to start values	(blood glucose 70-100				
	mg/dL at the start of				
	exercise AND <70 mg/dL				
	during or within 1hr after				
	exercise)				
Nocturnal hypoglycemia	Blood glucose <70 mg/dL	Wednesday 2:00-	A		
following exercise	for 30min of consecutive	3:15am			
	nocturnal readings				
Failure to adequately	Insulin bolus <120min	Thursday 7:14pm	A		
reduce pre-exercise	before start of exercise	Saturday 3:44pm			
bolus insulin	AND blood glucose <70				
	mg/dL during or within 1hr				
	after exercise				
Starting exercise with	Blood glucose >270	Friday 4:45pm	В		
elevated blood glucose	mg/dL at the start of	Sunday 4:17pm			
values	exercise				

August 13, 2024

Version #7

A, Based on this blood glucose data, it may be a good idea to review the recommendations from your healthcare professional about how you would adjust your food intake or insulin dosing around exercise. If you do not remember, it would be a good idea to reach out. B, If your blood sugar is high (more than 270 mg/dL) before starting exercise, check your blood or urine for ketones. If you test positive for ketones, avoid vigorous activity. If you do not have ketones in your blood or urine and you feel well, it should be fine to exercise.

Tool #4: Health outcome feedback regarding the causal impact of exercise upon blood glucose (Appendix 18). The GlucoseZone cloud will draw CGM metrics (coefficient of variation, mean, % time >180, 70-180, <70mg/dL) and covariates (insulin-on-board, carbohydrates self-reported into insulin device, exercise metrics including video selected and Fitbit minutes / heart rate / distance / calories / sleep / activity at sub-exercise intensity). The app organizes these data on a dashboard accessible to Yale staff. A Yale staff member exports the contents onto the Yale Secure Server weekly and enters them into our Bayesian R-code (Appendix 9b). The EP reviews the results and accompanying visualizations documenting a positive, neutral, or negative effect of exercise once per 1-4 weeks as insights are generated. The EP will message the client by encrypted emailed pdf relaying the most representative results and/or visualizations and any recommended adjustments by interpretating and applying exercise guidelines (e.g., "You have done purely resistance exercise for the past 28 days, and it has had the causal impact of increasing blood glucose time above target range. Consider more aerobic exercise.") If these EP's recommendations indicate repeating certain videos, they will accordingly appear on the home-screen the following week.

The mathematical basis of the R-code is our Bayesian time series model. Briefly, it compares CGM metrics over each 1-4 week period against a counterfactual predicted based upon the CGM during the 1-4 weeks before the period and the covariates over the 1-4 week period. The full formalism and an example of this analysis is available in our manuscript¹00. The advantage over linear modeling frameworks is the flexibility to evaluate the intervention's effect strength at all points in the intervention period. If p-values do not reach significance (α=.05) then the next version of the app will extend the length of the testing window before providing feedback, though even 1 week of CGM data at minimal adherence (70%) yields k=1,411 observations resulting in 96% power to detect a small effect size (d≥0.10) at α=.05. The maximum window of 4 weeks was chosen as a typical minimal frequency of health coaching sessions for long-term maintenance of lifestyle change¹01.

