For the 2-week familiarization period until visit 4, the trainer will review InPen data after days 1, 3, 7, 10, and 14 days to check if data are being transmitted consistently with reasonable values. The trainer will also talk with the participant at each visit and query of there are any issues or concerns. Trainer will follow up with participant to troubleshoot as needed. We will start with a bank of standard troubleshooting techniques from our procedure manual, then involve Medtronic customer service or a senior clinician from the research team as needed.

Participants will set up the Actigraph GT9X hip accelerometer (i.e., blinded hip and wrist watch) on their own belt, elastic waistband, or a belt we provide. They are asked to wear the device on the hip for all waking hours except bathing, and on the dominant wrist (i.e., opposite wrist of the Fitbit) for sleep. The device samples data at 30Hz and aggregates it into 60-second epochs. Non-wear periods are defined by Troiano's algorithm^94 confirmed against participant logs of non-wear periods; previously our wear time exceeded literature standards (14.1±1.9 waking hours per day for 5.4±1.0 out of 7 days). Participants will receive a daily morning SMS survey through Ilumivu or Qualtrics asking them to log that morning's attachment time and previous night's removal time.

Participants will measure blood pressure by standard home monitoring procedures. We will take the average of 2 brachial artery measurements after ≥12 hours abstention from acute blood pressure confounders (exercise, caffeine, alcohol, tobacco, nicotine) and ≥5 minutes of quiet rest using the Omron BP760N, which includes a rigid cuff that minimizes fitting errors. If the measurements differ by >5 mmHg, then a third will be taken and the closest two will be averaged. In the event of a result meeting the home BP monitoring criteria for uncontrolled accelerated hypertension (systolic >160 mmHg and/or diastolic >100 mmHg), the participant will be withheld from exercise participation until BP can be reassessed at least one day later. In the event of a second occasion meeting these values, the participant will be removed from the study and referred to their healthcare provider for follow-up.

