# 7.2 Planned Analyses

#### **Primary Objective 1 (DESCRIPTIVE).** Evaluate the intervention for feasibility

**Hypothesis 1-1.** Participant use metrics (i.e., % completion of diary, % wear-time of biosensors, frequency of video usage, % received of text messages) will be summarized with descriptive measures.

Primary Objective 2 (DESCRIPTIVE). Evaluate the intervention for acceptability (i.e., user satisfaction)

**Hypothesis 1-2.** Results of acceptability survey will be summarized with descriptive measures. Weekly interviews about app usage will be transcribed, reviewed, and analyzed by content analysis 105.

Primary Objective 3 (MACHINE LEARNING). Evaluate the mathematical robustness of the intervention by evaluating its performance to predict exercise behavior, assess exercise safety hazards, and measure exercise glycemic response.

Hypothesis 1-3-1. Predicting Exercise Behavior. The mathematical basis of the code is a binary classification model of exercise lapse using Python scikit-learn package v. 0.19.098, including random forests and gradient boosted tree ensembles (such as XgBoost99). We have completed analyses that train the model at the group level using the previous pilot dataset (section 1.2.3). These models have been pruned to reduce the complexity of the final classifiers and avoid overfitting the training data. This group-level model (Appendix 9a) will be the starting point for training a person-level model for each participant via supervised transfer learning methods during the present study to give the participant tailored prompts. This strategy mitigates the shortness of the timeframe (4 weeks) to train each person's model. At the end of the study, the data will first be used as an independent sample to validate the pilot group-level model. Second, they will be combined with the pilot data for a larger sample size to assess potential covariates, including pump vs. injection users, prior CGM usage, and age.

August 13, 2024 Version #7

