# **Tracking**

A. Daily monitoring during first 2 weeks for ketoacidosis, severe hypoglycemia, and other health risks associated with exercise:

We will detect any diabetic ketoacidosis or severe hypoglycemia within 24hr and suspend exercise until a personalized preventive strategy can be formed. To achieve this level of monitoring, a research assistant will monitor daily the biometric dashboard which contains Bluetooth-captured glucose, ketones, and exercise start/stop times. Safety signals include any of the following during or within 1hr of exercise: 1) Diabetic ketoacidosis (glucose ≥270 mg/dL + ketones ≥1.0 mmol/L), 2) Possible diabetic ketoacidosis (glucose ≥270 mg/dL and failure to test ketones), and 3) Possible severe hypoglycemia (glucose <55 mg/dL). Research staff will respond to each of these events within 24hr of its occurrence by informing the participant to immediately suspend the exercise program (app account will be suspended) until the participant has been contacted by a study physician. The physician will alert the participant and the participant's primary diabetes care provider to the issue and develop a prevention strategy, consulting with the primary diabetes care provider as needed. The exercise suspension will then be lifted, unless the participant has met the protocol's stoppage criteria (>1 episode of severe hypoglycemia, 1 episode of diabetic ketoacidosis not closely related to pump site failure).

In the event of the "possible" occurrences (#2, #3), physician contact can be replaced initially by research assistant contact to query symptoms. Then, if possible diabetic ketoacidosis is supported by the participant reporting symptoms, or possible severe hypoglycemia is supported by the participant reporting altered mental and/or physical status requiring assistance from another person for recovery, physician contact will be required as in paragraph #1 above.

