We will detect any other exercise-associated health risks within 24-36hr and suspend exercise until a personalized preventive strategy can be formed. To achieve this level of monitoring, the morning survey question about prior day's clinical events (Appendix 8a, last question) will be asked of participants and monitored by research staff daily. If the participant reports a clinical event, the PI will complete Adverse Event review and summary (c.f. Protocol Sect 6.3) the same day (i.e., within 24-36hr of the reported event). If the event may be exercise-related, the participant will be informed to immediately suspend the exercise program (app account will be suspended) until the participant has been contacted by a study physician. The physician will alert the participant to the issue and develop a prevention strategy, consulting with the participant's primary diabetes care provider as needed. The exercise suspension will then be lifted, unless the participant has met the protocol's stoppage criteria.

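### Days on which staff suspend exercise are not separated from behavioural lapses, so some lapse labels behind Hypothesis 1-3-1 can be protocol-imposed

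*Combined protocol and SAP*

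**What the plan says.** **The label.** Section 6.1.1, Visit 4, Tool #2 measures adherence by "usage of exercise guidance (videos or guided outdoor walking") and defines a lapse as the third miss in a week or the second "consecutive missed day given that the goal is 150 min/week spread over" at least five days. What makes a day 'missed' is not defined separately. The same section describes the pilot model as built "to predict exercise lapses (i.e., days without exercise"), which is a different label.

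**The holds.** Four routes impose days without exercise:
- Glucose or ketone signals (section 8.7, Tracking A): staff respond by "informing the participant to immediately suspend the exercise program (app account will be suspended) until the participant has been contacted by a study physician".
- Clinical events (section 8.7, Tracking A): "If the event may be exercise-related, the participant will be informed to immediately suspend the exercise program (app account will be suspended") until a study physician makes contact.
- High blood pressure (section 6.1.1, Visit 2, and section 8.7, Tracking C): "the participant will be withheld from exercise participation until BP can be reassessed at least one day later".
- Symptoms judged to indicate pathology (section 6.1.1, Monitor Symptoms, and section 8.7, Tracking C): exercise is suspended unless the primary care provider clears it.

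**The use of the label.** Section 7.2, Hypothesis 1-3-1, uses lapses to train person-level models and to validate the pilot group-level model. The criterion is an ROC AUC of .80, or a precision-recall AUC of .80 when lapses make up fewer than 20% of days. Hypothesis 1-1 separately reports "frequency of video usage" descriptively. Neither Tool #2, section 7.2 nor the missing-data section (7.7) mentions days under a hold, and hold status is not a listed predictor.

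**The concern.** A participant who is locked out of the app, or told not to exercise, cannot produce guided exercise that day. Under the lapse rule as written, the day is a miss. It may be a lapse itself, and it can also turn a later voluntary miss into a lapse, because it adds to the consecutive and weekly counts.

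Hypothesis 1-3-1 is meant to show that exercise behaviour can be predicted. Two distortions are possible, in opposite directions:
- Glucose both triggers some holds and feeds the predictors. A person-level model could therefore learn part of the suspension rule and look more accurate than it is.
- The pilot model, applied unchanged, could be marked down for failing to foresee staff decisions.

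There is also a practical consequence: nothing tells the message code to skip a participant who is on hold.

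**Working it through.** **Inputs from the documents.** Lapse rule and 5-day goal (6.1.1, Tool #2); 28-day intervention (section 4); pilot use of 2.4 app sessions per week (1.2.1); pilot random forest accuracy 79%, sensitivity 83%, specificity 71% (6.1.1, Tool #2); 21 expected completers (7.1). The documents give no hold rate, no hold length beyond at least one day for blood pressure, and no pilot AUC.

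**Step 1. Check the pilot figures.** The .80 is a chosen threshold, so there is nothing behind it to reproduce. The pilot figures do agree with each other. With one session per day assumed, the missed share is (7 − 2.4)/7 = .657, and accuracy = .83 × .657 + .71 × .343 = .789, against the stated 79%.

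**Step 2. New lapse days for one held participant.** I simulated the lapse rule over 28 days. Assumptions: independent days, one hold placed at random, and every missed day at or beyond the threshold counted. New share = (lapse days with hold − lapse days without) / lapse days with hold.

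| Exercise probability per day | No hold | 2-day hold (new share) | 3-day hold (new share) |
|---|---|---|---|
| 2.4/7 (pilot) | 14.35 | 15.27 (6%) | 15.73 (9%) |
| 1/2 | 9.00 | 10.30 (13%) | 10.94 (18%) |
| 5/7 (goal) | 3.05 | 4.60 (34%) | 5.46 (44%) |

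Example: (15.27 − 14.35)/15.27 = 6%. Held days as a share of all lapse-labelled days are 12% and 18% at pilot adherence, and 30% and 43% at the goal. A single held day is not automatically a lapse: it is labelled one about 78% of the time at pilot adherence and 38% at the goal.

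**Step 3. Pooled share.** Validation of the group-level model is pooled over participants. If 20% of participants had one 3-day hold (an assumption), new lapse days would be about 2% of the total and held days about 4% at pilot adherence. At the goal both would be about 14%.

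**Step 4. Effect on ROC AUC.** AUC = (1 − w) × A0 + w × Ah, where w is the held share of lapses, A0 the AUC on other lapses and Ah the AUC on held lapses. From the pilot sensitivity and specificity, an assumed range for A0 is (.83 + .71)/2 = .77 to .857 (binormal). The pilot label differs, so this range is rough.

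- Share needed to fall from .857 to .80 if held days are unpredictable (Ah = .5): .057/.357 = 16%.
- Share needed to rise from .77 to .80: .03/.23 = 13% if Ah = 1, or .03/.13 = 23% if Ah = .9.
- If A0 is already .79 to .81, about 3% to 9% is enough: .01/.31 = 3% downward from .81; .01/.21 = 5% to .01/.11 = 9% upward from .79.
- With the 4% held share in Step 3, the shift is .04 × (.5 − .857) = −.014 or .04 × (1 − .77) = +.009.

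This identity holds for ROC AUC only. At the 5-day goal about 11% of days are lapses, so the precision-recall criterion would apply, and this arithmetic does not size that case.

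**Step 5. Metric switch.** At pilot adherence about 51% of days are lapses (about 301 of 21 × 28 = 588), far from the 20% line. At 35% missed days the lapse rate is about 16%. It rises to about 19% with one 1-day hold per participant and about 25% with one 3-day hold each, so multi-day holds could change the metric there.

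**The case against.** The strongest reply is that scoring holds as lapses is inferred from silence. The plan defines a lapse but not a missed day, and the code (Appendix 9a) is not among the documents. That is right: the plan leaves the point open and does not state that held days are lapses.

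Several limits on size also stand:
- Participants are sedentary at entry and the pilot rate was 2.4 sessions a week, so the 34% to 44% figures describe a favourable adherence scenario.
- A glucose signal arises during or within an hour of exercise, so the signal day is normally an exercise day. A one-day hold after it is a lapse only if it is the third miss that week. The simulation does not build this in.
- For the signals classed as possible events, research-assistant contact can initially replace physician contact, and avoidable musculoskeletal complaints need not stop exercise.
- The daily glucose review is described as covering the first 14 days of the trial (2.2), while the app starts on Day 22. However, Tool #2 has staff review the dashboard daily while generating messages, and the signals are tied to exercise and app suspension. Weekly blood pressure and symptom checks run to Visit 10.
- The glucose predictors are 24-hour summaries, and ketones, blood pressure and symptoms are not listed predictors. Perfect ranking of held days is therefore an upper bound.

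A reader might also infer that only the exercise physiologist's edit stands between a held participant and an encouragement message. The documents do not establish this: the code is run by the person doing the safety review, and messages travel through an app account that some holds suspend. A reader might further infer that video use must exclude held days. Hypothesis 1-1 has no pass threshold, and use lost to safety holds is real feasibility information.

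**Conclusion.** The gap is real: the lapse rule, read literally, takes in staff-imposed days without exercise, and nothing removes or flags them in a primary-objective outcome. The resulting label error may be informative, because glucose sits on both sides, and it can move the AUC up or down.

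Its size is conditional. Per held participant, new lapse days are about 6% to 9% of lapse days at pilot adherence and 34% to 44% at the 5-day goal, for 2- and 3-day holds, assuming independent days and one session per day. It is tempting to conclude that holds will decide Hypothesis 1-3-1. The documents do not support that: no hold rate is given, and at pilot adherence the held share reaches 18% only if every participant has a 3-day hold. The effect on the pooled verdict is likely small unless holds are common or the AUC is already near .80. The change is worth making because it is cheap and removes the ambiguity before the data are seen.

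**What to change.** 1. Define a missed day in section 6.1.1 (Tool #2) and section 7.2.
2. Record the start, stop and reason of every hold (glucose or ketone, clinical event, blood pressure, symptoms) in the dashboard export that staff already make daily.
3. Treat held days as not at risk: exclude them from the lapse label, from the consecutive and weekly missed-day counts, from person-level training and from validation for Hypothesis 1-3-1.
4. Do not run the encouragement-message code on held days.
5. Report AUC with and without held days.
6. Report the number and length of holds, and give video use both over all days and over eligible days.

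The cost is a hold record in an existing export, a few sentences of analysis text and slightly fewer person-days for training and validation. The safety rules stay as they are.
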